5.4.1.2. Continuous Endpoints

5.4.1.2.1. HBsAg, HBeAg, HBV DNA and ALT

Actual values (original unit and \log_{10} transformed values), changes from baseline (\log_{10} transformed values) and changes from RT (\log_{10} transformed values) over time in HBsAg, HBeAg, HBV DNA and ALT (actual values only) will be evaluated.

Change from baseline is defined as the value at a given time point minus baseline value.

The change from baseline value to the nadir (i.e. maximum decrease for each participant) in HBsAg, HBeAg, and HBV DNA will be evaluated at five intervals: treatment period 1 nadir (first 12 weeks of treatment), treatment period 2 nadir (second 12 weeks of treatment), on-treatment nadir (first 24 weeks), during follow-up nadir, and entire study nadir.

Only HBeAg positive participants will be used for the analysis of HBeAg values and changes from baseline.

5.4.1.3. Time to Event Endpoints

5.4.1.3.1. Time to First HBsAg Seroclearance

Time to HBsAg seroclearance is defined as the number of days between the date of first study intervention intake and the date of the first occurrence of HBsAg seroclearance (i.e. the date of the first HBsAg seroclearance – the date of first study intervention intake + 1). The participants who withdrew early from the study before achieving HBsAg seroclearance or who did not achieve HBsAg seroclearance will be censored at the last available HBsAg assessment.

Time to HBsAg seroclearance will be also analyzed considering the participants who were retreated with NA before achieving HBsAg seroclearance as censored at the date of NA retreatment.

In addition, time to the first occurrence of the following events (i.e. the date of the first occurrence of the event – the date of first study intervention intake + 1) will be analyzed:

- HBsAg <100 IU/mL
- HBsAg decline $\geq 1.0 \log_{10}$ IU/mL
- HBsAg decline $\geq 2.0 \log_{10}$ IU/mL
- HBsAg decline $\geq 3.0 \log_{10}$ IU/mL

Time to the first occurrence of the events above will be also analyzed considering the participants who were retreated with NA before achieving the event as censored at the date of NA retreatment.

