9.4.2.2. Secondary Efficacy Endpoints

Descriptive statistics and 90% CIs will be used to summarize all efficacy endpoints.

Specific key selected endpoints may be analyzed using suitable categorical data approaches (eg, Clopper-Pearson interval or logistic regression for proportions or other categorical type of endpoint), longitudinal repeated measures models (eg, for continuous types of variables), or survival analysis based on the Kaplan-Meier estimates (for time-to-event variables), as appropriate.

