5.1.6. Analysis Specifications

In general, continuous variables will be summarized using descriptive statistics including the number of participants, mean, standard deviation (SD), two-sided 90% confidence interval (CI), median, and range. The 90% CI for continuous endpoints is constructed using the t-distribution. Binary or categorical variables will be summarized using the number and percentage of participants in each category and 90% CI using Clopper-Pearson exact method for the single sample proportion (Newcombe 1998). For time-to-event variables, using the Kaplan-Meier approach, a summary table including number of participants included in the analysis, number of participants censored, 25th and 75th percentiles, median time-to event and 90% CI will be shown. Graphic displays will also be used to summarize the data.

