5.4.1.3.3. Time to First HBeAg Seroclearance

Seroclearance of HBeAg is defined as (quantitative) HBeAg level < LLOQ.

Time to first HBeAg seroclearance is defined as the number of days between the date of first study intervention intake and the date of the first occurrence of HBeAg seroclearance (i.e. the date of the first HBeAg seroclearance – the date of first study intervention intake + 1). The participants who withdrew early from the study before achieving HBeAg < LLOQ or who did not achieve HBeAg < LLOQ will be censored at the last available HBeAg assessment.

Time to first HBeAg seroclearance will be also analyzed considering the participants who were retreated with NA before achieving HBeAg seroclearance as censored at the date of NA retreatment.

Time to first HBeAg seroclearance will be calculated only for HBeAg positive participants.

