5.4.2.3. Time to Event Endpoints

The Kaplan-Meier method will be used to estimate and plot the cumulative incidence and estimate the median time with 90% CI. In addition, the number and percentage of participants who had an event or were censored will be reported.

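### Kaplan-Meier curves that censor at NA re-treatment are labelled cumulative incidence; for HBsAg seroclearance and seroconversion they can overstate, and never understate, response without re-treatment

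*SAP*

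**What the plan says.** SAP 5.4.1.3.1 defines time to first HBsAg seroclearance from first intake of study intervention, in two versions. In the first, NA re-treatment plays no part: those "who did not achieve HBsAg seroclearance will be censored at the last available HBsAg assessment". In the second, participants are handled as "retreated with NA before achieving HBsAg seroclearance as censored at the date of NA retreatment". The HBsAg thresholds in the same section (level below 100 IU/mL; declines of at least 1, 2 and 3 log10) get a matching second version, with participants "retreated with NA before achieving the event as censored at the date of NA retreatment".

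The rule recurs for HBsAg seroconversion (5.4.1.3.2), HBeAg seroclearance and seroconversion (5.4.1.3.3, 5.4.1.3.4), HBV DNA <LLOQ (5.4.1.3.5) and the exploratory HBV RNA, HBcrAg, anti-HBs and anti-HBe endpoints (5.5.1.3). The sentence in 5.4.1.3.2 is garbled, so it is unclear whether censoring at re-treatment is the additional version or the only one for HBsAg seroconversion.

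On estimation, SAP 5.4.2.3 says: "The Kaplan-Meier method will be used to estimate and plot the cumulative incidence and estimate the median time with 90% CI". SAP 5.5.2.3 carries this to the exploratory endpoints, and Protocol 9.4.2.2 and SAP 5.1.6 also name only Kaplan-Meier. Neither document mentions a competing-risk estimator, a hypothetical estimand or an independent-censoring assumption.

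**The concern.** Kaplan-Meier assumes that a censored participant has the same future chance of the event as those who remain at risk. Protocol 6.7.1 re-starts NA for raised HBV DNA, for raised HBV DNA together with raised ALT, for HBeAg seroreversion, or for declining liver function. These are relapse events, so the censoring is informative.

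The SAP's own binary definitions treat re-treatment as the end of the chance to respond: off-treatment seroclearance (5.4.1.1.4.2) and functional cure (5.4.1.1.5) both require that NA was not re-started. The censored curve instead redistributes the re-treated participant's probability to those still at risk, as if that participant might yet respond without re-treatment. One report could therefore show different rates of seroclearance without re-treatment for the same people.

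Time to seroclearance and seroconversion are listed secondary endpoints (SAP 1.1). With a single arm the estimated level is itself the result, and no control arm would cancel a one-directional error.

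**Working it through.** **The plan's own figure.** No number is stated for the time-to-event analyses, and no rate of seroclearance or re-treatment is assumed anywhere. The only sizing figure is the two-sided 90% Clopper-Pearson interval. For 25/50, exact beta quantiles give 0.376 to 0.624 (width 0.248), as in SAP section 3; the other table entries also reproduce.

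**Inputs.** N = 50 is the planned size (SAP 1.2). Event and re-treatment counts are assumptions. There is no other censoring. All R re-treatments fall at one time, with E1 events before it and E2 after.

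**Formulas.**
- 1-KM with re-treatment censored = 1 − (1 − E1/N) × (1 − E2/(N − E1 − R))
- Aalen-Johansen cumulative incidence, re-treatment competing = (E1 + E2)/N

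The two agree if R = 0 or E2 = 0. Otherwise 1-KM is larger, because the later events are divided by a risk set from which the re-treated have been removed.

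**Results for 4 events.** Cumulative incidence is 4/50 = 8.0% in every row.

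| Early, late events | 1-KM, R = 8 | 1-KM, R = 20 |
|---|---|---|
| 4, 0 | 8.0% | 8.0% |
| 3, 1 | 1 − 0.94 × 38/39 = 8.4% | 1 − 0.94 × 26/27 = 9.5% |
| 2, 2 | 1 − 0.96 × 38/40 = 8.8% | 1 − 0.96 × 26/28 = 10.9% |
| 0, 4 | 4/42 = 9.5% | 4/30 = 13.3% |

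The last row is the worst-case ordering. The clock starts at first dose, so on-treatment seroclearances count as early events and pull the result towards the upper rows.

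**Spread-out event times.** In 2,000 simulated trials of 50, with assumed constant 48-week cumulative hazards of 0.15 (seroclearance) and 0.40 (re-treatment), mean 1-KM was 13.8% against a mean cumulative incidence of 11.4%. In no run was 1-KM the lower. The closed forms agree: 1 − exp(−0.15) = 13.9%, and (0.15/0.55) × (1 − exp(−0.55)) = 11.5%.

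**Which endpoints are exposed.** Only participants who stopped NA can be re-treated. Planned stopping requires, at Week 24, HBsAg <10 IU/mL, HBeAg-negative status, HBV DNA <LLOQ and ALT <3x ULN (Protocol 6.6, SAP 5.4.1.1.1). The rule censors only those re-treated before the event.
- Near zero: HBV DNA <LLOQ, HBsAg <100 IU/mL and HBeAg seroclearance, because planned stoppers have already had these events. The same is essentially true of the 1 log10 HBsAg decline, since entry required screening HBsAg >100 IU/mL (criterion A13.1).
- Exposed: HBsAg seroclearance and seroconversion, the larger HBsAg declines, and some exploratory markers (HBV RNA, HBcrAg, antibodies), because the stopping criteria do not imply them.

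**The case against.** **The question is already answered without Kaplan-Meier.** The Week 48 endpoint and functional cure are binary and exclude re-treated participants from response (SAP 5.4.1.1.4.2, 5.4.1.1.5, 5.4.2.1.3.2, 5.4.2.1.4). SAP 5.4.2.3 also prints the number and percentage with an event, which is 4/50 = 8.0% in the example above. This stands, and it limits the consequence. It does not make the plotted curve correct, and the raw percentage equals the cumulative incidence only when nobody drops out earlier for other reasons.

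**The version is supplementary and could be a hypothetical estimand.** It might be read as the course had NA not been re-started. The SAP does not say so, that reading needs independent censoring, which relapse-triggered re-start makes implausible, and cumulative incidence would be the wrong label for it. Re-start at the investigator's discretion below the cut-offs is allowed, so not every re-treatment is a criterion-defined failure; it still ends the chance of a response without re-treatment.

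**The excess is small against sampling error.** The exact 90% CI for 4/50 is 2.8% to 17.4%, and the study is exploratory with no formal hypothesis. This stands too. Twenty re-treatments would need at least 20 of 50 to stop NA and later re-start, a rate the documents do not support or exclude.

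**Stronger readings to avoid.** A reader might infer that the bias is always present, that every censored version is distorted, or that the functional-cure result is inflated. The excess is zero when nobody is re-treated or all events come first; several versions are almost untouched because of the stopping criteria; and functional cure is a separate binary endpoint. Time to first seroclearance is not a proxy for it, since it counts transient and on-treatment clearance and includes participants who stay on NA.

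**Conclusion.** The point holds for the versions that censor at NA re-treatment, and there only. Read as the cumulative incidence of response without re-treatment, their 1-KM curves are never too low, and are too high whenever an event follows a re-treatment. That conclusion needs only the SAP's censoring rule and estimator; the direction does not depend on any assumed rate.

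The size does. With the assumed 50 participants, 4 events and 8 re-treatments the excess is 0 to 1.5 percentage points (9.5 − 8.0); with 20 re-treatments it reaches 5.3 points (13.3 − 8.0) in the worst ordering. Participants who continue NA stay in the risk set and dilute the effect in the full analysis set.

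The primary endpoint, the uncensored time-to-event versions and the binary Week 48 and functional-cure analyses are unaffected. This is a worthwhile correction to secondary and exploratory outputs, not a threat to the study's main conclusions.

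**What to change.** In SAP 5.4.2.3, and through it 5.5.2.3, state that the versions now censored at NA re-treatment will use the Aalen-Johansen cumulative incidence, with NA re-treatment as a competing event and 90% CIs at Follow-up Weeks 24 and 48. Keep the uncensored Kaplan-Meier version beside it. Repair the sentence in 5.4.1.3.2 so that both versions of HBsAg seroconversion are clear. If a hypothetical reading is in fact intended, say so, state the independent-censoring assumption, and drop the cumulative-incidence label for that curve.

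The cost is SAP wording and a standard software option; trial conduct and data collection do not change. The downside is that median times may not be estimable from these curves, so the incidence at the two follow-up weeks would be reported in their place.

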5.4.1.3.2. Time to First HBsAg Seroconversion

Time to first HBsAg seroconversion is defined as the number of days between the date of first study intervention intake and the date of the first occurrence of HBsAg seroclearance and appearance of anti-HBs antibodies (i.e. the date of the first HBsAg seroclearance and anti-HBs

antibodies – the date of first study intervention intake + 1). The participants who withdrew early from the study before achieving HBsAg seroclearance and anti-HBs antibodies or who did not achieve HBsAg seroclearance and anti-HBs antibodies will be censored at the last available anti-HBs antibodies assessment.

Time to first HBsAg seroconversion will be the participants who were retreated with NA before achieving HBsAg seroclearance and anti-HBs antibodies will be censored at the date of NA retreatment.

5.4.1.3.3. Time to First HBeAg Seroclearance

Seroclearance of HBeAg is defined as (quantitative) HBeAg level < LLOQ.

Time to first HBeAg seroclearance is defined as the number of days between the date of first study intervention intake and the date of the first occurrence of HBeAg seroclearance (i.e. the date of the first HBeAg seroclearance – the date of first study intervention intake + 1). The participants who withdrew early from the study before achieving HBeAg < LLOQ or who did not achieve HBeAg < LLOQ will be censored at the last available HBeAg assessment.

Time to first HBeAg seroclearance will be also analyzed considering the participants who were retreated with NA before achieving HBeAg seroclearance as censored at the date of NA retreatment.

Time to first HBeAg seroclearance will be calculated only for HBeAg positive participants.

5.4.1.3.4. Time to First HBeAg Seroconversion

Time to first HBeAg seroconversion is defined as the number of days between the date of first study intervention intake and the date of the first occurrence of HBeAg seroclearance and appearance of anti-HBe antibodies (i.e. the date of the first HBeAg seroclearance and anti-HBe antibodies – the date of first study intervention intake + 1). who withdrew early from the study before achieving HBeAg seroclearance and anti-HBe antibodies or who did not achieve HBeAg seroclearance and anti-HBe antibodies will be censored at the last available anti-HBe antibodies assessment.

Time to first HBeAg seroconversion will be also analyzed considering the participants who were retreated with NA before achieving HBeAg seroclearance and anti-HBe antibodies as censored at the date of NA retreatment.

Time to first HBeAg seroconversion will be calculated only for HBeAg positive participants.

5.4.1.3.5. Time to First HBV DNA < LLOQ

Time to first HBV DNA < LLOQ is defined as the number of days between the date of first study intervention intake and the date of the first occurrence of HBV DNA < LLOQ (i.e. the date of the first HBV DNA < LLOQ – the date of first study intervention intake + 1). The participants who withdrew early from the study before achieving HBV DNA < LLOQ or who did not achieve HBV DNA < LLOQ will be censored at the last available HBV DNA assessment.

Time to first HBV DNA < LLOQ will be also analyzed considering the participants who were retreated with NA before achieving HBV DNA < LLOQ as censored at the date of NA retreatment.

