In currently not treated HBeAg-positive participants (mean baseline HBV DNA levels 7.65 to 8.24 \log_{10} IU/mL), there were pronounced declines in mean (standard error [SE]) HBV DNA from baseline of 5.53 (0.23) and 5.88 (0.34) \log_{10} IU/mL for JNJ-6379 75 mg and 250 mg + NA, respectively, and 5.21 (0.42) \log_{10} IU/mL for placebo + NA. In currently not treated HBeAg-negative participants (mean baseline HBV DNA levels 4.89 to 5.40 \log_{10} IU/mL), interpretation of mean (SE) HBV DNA decline was confounded since many participants had HBV DNA < lower limit of quantification (LLOQ) from Week 4 onwards.

In currently not treated participants, JNJ-6379 75 mg and 250 mg + NA showed a clear mean (SE) HBV RNA decline from baseline (2.82 [0.25] and 3.13 [0.35] \log_{10} copies/mL, respectively) compared with placebo + NA (1.43 [0.32] \log_{10} copies/mL), thereby differentiating JNJ-6379 from

NAs. HBV RNA was target not detected (TND) at Week 24 in 16/27 (59%), 19/25 (76%) and 9/20 (45%) participants, respectively.

The 24-week interim efficacy data in virologically suppressed participants showed that most participants had HBV DNA levels below the limit of quantification at baseline. All virologically suppressed participants on JNJ-6379 + NA who had detectable HBV RNA at baseline achieved HBV RNA TND at Week 24 (13/13 participants on 75 mg JNJ-6379 and 8/8 participants on 250 mg JNJ-6379) vs 1/7 (14%) participants on placebo + NA.

In currently not treated HBeAg-positive participants, JNJ-6379 75 mg and 250 mg + NA resulted in a mean (SE) HBsAg decline of 0.13 (0.10) and 0.40 (0.15) \log_{10} IU/mL, respectively, compared with 0.22 (0.11) for placebo + NA at Week 24. Participants with HBsAg declines also had HBeAg declines and frequently had early on-treatment isolated ALT flares. In both JNJ-6379 + NA arms:

- Maximal individual HBsAg and HBeAg reductions were 1.28 and 1.8 \log_{10} IU/mL, respectively, at Week 24;
- The proportion of currently not treated HBeAg-positive participants with $>0.3 \log_{10}$ IU/mL reductions from baseline in:
 - HBsAg was 8/23 (35%) vs 1/8 (13%) for placebo + NA;
 - HBeAg was 19/23 (83%) vs 4/8 (50%) for placebo + NA;
- The proportion of virologically suppressed HBeAg-positive participants with $>0.3 \log_{10}$ IU/mL reductions in HBeAg was 7/19 (37%) vs 1/5 (20%) for placebo + NA.

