5.1. Inclusion Criteria

Each potential participant must satisfy all of the following criteria to be enrolled in the study:

A01 Male or female participants ≥ 18 years of age (or older if the legal age of consent in the jurisdiction in which the study is taking place is >18) to ≤ 65 years of age.
(adapted from M01)

M02 Participants must be medically stable based on physical examination, medical history, vital signs, and 12-lead ECG performed at screening. If there are abnormalities, they must be consistent with the underlying illness in the study population. This determination must be recorded in the participant’s source documents and initialed by the investigator.

A03 (adapted from M03a) Participants must have chronic HBV infection. HBV infection must be documented by serum HBsAg positivity at screening. In addition, chronicity must be documented by any of the following, at least 6 months prior to screening: serum HBsAg positivity, HBeAg positivity or HBV DNA positivity, ALT elevation above ULN without another cause than HBV infection, documented transmission event. If none of the above are available, the following ways of documenting chronicity are acceptable at the time of screening: liver biopsy with changes consistent with chronic HBV, or absence of marker for acute HBV infection such as positive immunoglobulin M (IgM) anti-hepatitis B surface (HBs) and anti-HBc antibodies.

Participants should:

- be on stable HBV treatment, defined as currently receiving NA treatment for at least 6 months prior to screening and having been on the same NA treatment regimen (at the same dose) as used in this study for at least 3 months at the time of screening, AND
- have serum HBV DNA <60 IU/mL on 2 sequential measurements at least 6 months apart (one of which is at screening), AND
- have documented ALT values <2.0x ULN on 2 sequential measurements at least 6 months apart (one of which is at screening).

M04 Participants must have a body mass index (BMI; weight in kg divided by the square of height in meters) between 18.0 and 35.0 kg/m², extremes included.

A05 (adapted from M05) Participants must sign a Master ICF (specific for the Master Protocol PLATFORMPAHPB2001) and must sign an ICF specific for this intervention cohort, indicating that he or she understands the purpose of, and procedures required for, the study and is willing to participate in the study.

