5.1.9. Data Handling Rules

Those measurements collected from screening visit to the end of study will be handled according to the following rules summarized in [Table 5](#).

Table 5: Data Handling Rules for HBV Virology and Serology Assessments

HBV parameter	LLOQ	ULOQ	Imputed Values	
			If value < LLOQ	If value > ULOQ
HBsAg	0.05 IU/mL	249,750.00 IU/mL with dilution	0.025 IU/mL ^(a)	274,725.00 IU/mL ^(b) with dilution
HBeAg	0.11 IU/mL	7,000.00 IU/mL with dilution	0.055 IU/mL ^(a)	7,700.00 IU/mL ^(b) with dilution
HBcrAg*	3.0 log ₁₀ U/mL	9.0 log ₁₀ U/mL with dilution	2.7 log ₁₀ U/mL	9.9 log ₁₀ U/mL ^(b) with dilution
HBV DNA	20 IU/mL	170,000,000 IU/mL w/o dilution	If target detected: 15 IU/mL If target not detected: 5 IU/mL**	187,000,000 ^{(b)(c)} IU/mL w/o dilution
HBV RNA*	LLOQ = 2.939 log ₁₀ cp/mL (i.e. 869 cp/mL) LOD = 1.398 log ₁₀ cp/mL (i.e. 25 cp/mL)	NAP	If <LOD or target not detected then 1.114 log ₁₀ cp/mL (i.e. 13 cp/mL)	NAP
Anti-HBs	5 mIU/mL	10,000.0 mIU/mL	2.5 mIU/mL ^(a)	11,000.0 mIU/mL ^(b)

* As new assays become available different data handling rules may apply.

** For HBV DNA <LLOQ: Spaghetti plots showing absolute values, the imputed value will be 15 IU/mL for both target detected, and target not detected. All other tables, listings, and figures will be produced using 15 IU/mL as an imputed value if target is detected and 5 IU/mL if target is not detected.

Key: NAP=Not applicable

(a) LLOQ/2

(b) ULOQ+(ULOQ/10)

(c) If the original result > ULOQ, then take the re-test value (i.e. diluted result). If the diluted result is not available, use the imputed value indicated in this table

All other viral activity data with values <LLOQ which are not included in the data handling rules above will be imputed by the absolute value divided by 2.

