5.4.2. Analysis Methods

All secondary endpoints will be analyzed using the FAS. The analysis may be repeated in the IFN-FAS and modified FAS/IFN-FAS analysis sets if there is a difference of at least 2 participants between analysis sets.

Some analysis will be performed by group, as defined in Section 5.1.10. Summaries and graphs will be provided for each analysis phase, unless specified otherwise.

All secondary endpoints will be analyzed based on the observed case data. Additional analyses with specific imputation methods for missing data are added for selected endpoints.

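### Time to first HBV DNA <LLOQ has no at-risk restriction in a trial of virologically suppressed patients, so its Kaplan-Meier median would reflect entry status or the visit schedule

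*SAP*

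**What the plan says.** SAP 5.4.1.3.5 states: "Time to first HBV DNA < LLOQ is defined as the number of days between the date of first study intervention intake" and the first HBV DNA result below LLOQ, calculated as event date minus first intake date plus 1. Participants without the event are censored at their last HBV DNA assessment. A second version also censors at NA re-treatment. Neither version sets a baseline condition, and the SAP does not say whether a baseline value can be the event.

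SAP 5.4.2 says "All secondary endpoints will be analyzed using the FAS"; that set is every enrolled and dosed participant (SAP 4, Table 2). SAP 5.4.2.3 applies Kaplan-Meier, with a median and 90% CI.

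On who enters, inclusion criterion A03 (Protocol 5.1) requires participants to "be on stable HBV treatment, defined as currently receiving NA treatment for at least 6 months prior to screening" and to "have serum HBV DNA <60 IU/mL on 2 sequential measurements at least 6 months apart", one of the two at screening. SAP Table 5 gives the assay limit: "HBV DNA 20 IU/mL".

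For a parallel endpoint the SAP does restrict: "Time to first HBeAg seroclearance will be calculated only for HBeAg positive participants" (SAP 5.4.1.3.3).

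**The concern.** A time-to-event analysis should start with people who do not yet have the event. Here eligibility selects people who mostly do. The protocol reports, for suppressed participants in the sponsor's own Phase 2a study of JNJ-6379, that "most participants had HBV DNA levels below the limit of quantification at baseline" (Protocol 2.2.3.1).

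The endpoint is among the secondary endpoints in the protocol. Run as written, it would show early and widespread achievement of HBV DNA <LLOQ. A reader could take that as a treatment effect, although it was produced by NA therapy before the trial. Because the SAP does not say whether baseline counts, two programmers could also report medians of 1 and 29 days from the same data.

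**Working it through.** **Plan's own figures.** None is given for this endpoint. The SAP's only quantitative design figures are the Clopper-Pearson 90% intervals in Table 1. They reproduce to three decimals (25 of 50: 0.376 to 0.624, width 0.248). I take N = 50 from there.

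**Inputs.**
- Eligibility ceiling: 60 IU/mL (Protocol 5.1, A03). LLOQ: 20 IU/mL (SAP Table 5). An eligible participant is therefore below 20 IU/mL, with the event already present, or at 20 to below 60 IU/mL.
- HBV DNA samples: screening, Day 1 before dosing, then Week 4, which is Day 29 ± 2. There is none at Week 2 (Protocol 1.3).
- Share below LLOQ at baseline, *s*: not stated for this trial. Assumed 50% to 95%.

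**Reading (a): the Day 1 pre-dose sample counts.** Event date equals first intake date, so time = 0 + 1 = 1 day. Cumulative incidence on Day 1 equals *s*, and the median is Day 1 whenever *s* is at least 50%.

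| *s* | Below LLOQ at baseline, of 50 | KM incidence, Day 1 | Median | At risk if restricted |
|---|---|---|---|---|
| 50% | 25 | 0.50 | Day 1 | 25 |
| 60% | 30 | 0.60 | Day 1 | 20 |
| 70% | 35 | 0.70 | Day 1 | 15 |
| 80% | 40 | 0.80 | Day 1 | 10 |
| 90% | 45 | 0.90 | Day 1 | 5 |
| 95% | 48 (47.5 rounded) | 0.96 | Day 1 | 2 |

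If a screening value 28 days before first intake were allowed to count, the formula would give −28 + 1 = −27 days.

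**Reading (b): only post-dose samples count.** A participant who simply stays suppressed has the event at the first scheduled sample, Day 29 (27 to 31). For illustration, assume a 95% chance per visit of being below LLOQ if below it at baseline, and 40% otherwise. Expected incidence at Day 29 is 0.95*s* + 0.40(1 − *s*):
- *s* = 70%: 0.665 + 0.120 = 0.785
- *s* = 80%: 0.760 + 0.080 = 0.840
- *s* = 90%: 0.855 + 0.040 = 0.895

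A simulation with N = 50 gave 0.786, 0.840 and 0.894, with median Day 29 each time. Among those at or above LLOQ at baseline, incidence is 0.40 at Day 29 and 1 − 0.60² = 0.64 at Day 57, so their median is Day 57. The unrestricted median hides this group.

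**How the SAP treats the parallel endpoints.**

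| Endpoint | Protection against having the event at entry |
|---|---|
| HBeAg seroclearance, seroconversion (5.4.1.3.3, 5.4.1.3.4) | HBeAg-positive only |
| HBV RNA <LOD (5.5.1.3.1) | Baseline at least LOD + 0.5 log10 |
| HBcrAg undetectability (5.5.1.3.2) | Baseline at least 3.5 log10 U/mL |
| Anti-HBs appearance (5.5.1.3.3) | Baseline below LLOQ is part of the definition |
| Anti-HBe appearance (5.5.1.3.4) | Anti-HBe negative only |
| HBsAg seroclearance, HBsAg <100 IU/mL (5.4.1.3.1) | Eligibility requires more than 100 IU/mL at screening |
| HBV DNA <LLOQ (5.4.1.3.5) | None |

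**The version censored at NA re-treatment.** Stopping NA under the completion criteria itself requires HBV DNA <LLOQ at Week 24 (Protocol 6.6). Anyone re-treated after stopping that way has already had the event. This censoring can affect only participants who stopped NA outside those criteria.

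**The case against.** The strongest counter-argument has four parts.

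- **The baseline share is inferred.** Participants at 20 to below 60 IU/mL are eligible, and the supporting sentence comes from another study, without a percentage or an assay limit. This stands as a caveat. The conclusion needs only that about half are below LLOQ, which prior NA therapy and the protocol's own remark make likely.
- **The 1-day result depends on the reading.** It arises only if a pre-dose sample can be the event, which the SAP does not say. That is correct, but the other reading moves the problem to Day 29. That day is also not absolute: the visit window is ± 2 days, unscheduled visits are allowed, and half must be below LLOQ by then.
- **The consequence is small.** The study is exploratory with no formal test, and no decision rule in the documents rests on this endpoint. Baseline HBV DNA categories (SAP 6.3.2) and proportions below LLOQ over time (SAP 5.4.2.1.10) will be tabulated. This limits severity, but a table beside an uninformative median does not correct it.
- **The 10% minimum is borrowed.** The SAP uses 10% for other purposes, such as a descriptive anti-HBs subset (5.5.2.2.3), never as a number at risk for Kaplan-Meier. That is fair; it is a convenient convention here, and a curve on 5 people says little.

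**Conclusion.** The concern holds. No section of either document adds the restriction or says whether a baseline value counts. With an assumed 60% to 95% below LLOQ at entry, the plan yields 60% to 95% incidence on Day 1 and a median of 1 day, or a median at the first scheduled post-dose sample. Both results come from prior NA therapy and the sampling schedule. They rest on at least half the participants being below 20 IU/mL at the relevant sample, which the documents support but do not quantify. This should be corrected because it is a secondary endpoint named in the protocol. It does not threaten the primary endpoint or any formal inference.

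**What to change.** Amend SAP 5.4.1.3.5 to include only participants with baseline HBV DNA at or above LLOQ (20 IU/mL), count post-baseline results only, and report how many qualify. If fewer than 10% (5 of 50) qualify, give a listing in place of Kaplan-Meier. Apply the same set to the version censored at NA re-treatment, or drop that version.

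The definition needs about one sentence. The protocol's objectives table limits HBeAg but not HBV DNA, so the restriction should also be recorded in SAP Appendix 2, which now reports no changes from the protocol.

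The price is a small set: 2 to 10 of 50 if 80% to 95% are below LLOQ at baseline, possibly enough only for a listing. Little is lost, since suppression on and off treatment remains covered by the proportions below LLOQ in SAP 5.4.2.1.10.
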